16.3.1. Analysis of Primary Outcome

The outcome for each arm will be the proportion of subjects classified as a success. Each of the two experimental arms will be compared separately to the control arm (Arm A) at the appropriate timeframes. All randomized subjects will be included in the comparisons according to their randomized arm (ITT analysis). The statistical significance of each comparison will be based on the odds ratio using exact computations for stratified 2x2 frequency tables and using Monte Carlo estimation if necessary. The stratifier will be clinical site, with the possibility of pooling clinical sites having a small contribution. If cytisinicline is not favored by the effect size point estimate then the comparison will be designated as not statistically significant.

The estimated common odds ratio and its exact confidence interval will be reported. In addition, the estimated odds ratio and exact confidence interval for the marginal 2x2 table across sites (unadjusted odds ratio), and the estimated difference in proportions and the associated derived exact confidence interval using the exact confidence interval on the odds ratio will be reported. The exact difference in proportion confidence interval is derived using the method of Thomas (1971 and 1977).^{18,19}

The primary comparisons will be presented in the context of a tipping point analysis.²⁰ Other supporting and sensitivity analyses challenging the results as well as analyses designed to assess homogeneity of effect are planned and described in the SAP.

16.4. Secondary Outcome for Subjects

The secondary efficacy outcome 1 and 2 (continued biochemically verified abstinence to Week 24) for each subject is binary: success versus failure. Success is defined for the subject as having reported smoking abstinence since the last clinic visit at each clinic assessment from Week 6 (Arm B) or Week 12 (Arm C) to Week 24 with biochemical verification at each assessment. Biochemical verification will be defined by a carbon monoxide concentration in exhaled breath of less than 10 ppm. During the Follow-up Smoking Cessation Assessment Period between Weeks 12 to 24, self-report of smoking abstinence will be according to the Russell Standard.¹⁷

The secondary efficacy outcome 3 is success with respect to being without relapse at Week 24. The secondary efficacy outcome 3 (reduction in risk of relapse from Week 6 to Week 24 in Arm C vs Arm B) will be assessed in each subject (in both Arms C and B). Subjects not abstinent at Week 6 will be regarded as having relapsed.

The considerations relative to the definition of these secondary efficacy endpoints are similar. The analyses associated with these three objectives will be done as Intent-to-Treat (ITT) analyses. The statistical model used for secondary objectives will be the same statistical model used for the analysis of the primary objectives.

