7.2. Treatment Period (12 Weeks)

Treatment Period must begin on the day after randomization. Study treatment will be blinded, and subjects will take one study tablet three times during the day, approximately 5 hours apart. Subjects randomly assigned to Arm A will take one placebo tablet at each dosing per day for 12 weeks. Arm B subjects will take one cytisinicline tablet at each dosing per day for the first 6 weeks followed by one placebo tablet at each dosing per day for the last 6 weeks. Arm C subjects will take one cytisinicline tablet at each dosing per day for 12 weeks.

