16.5. Study Size

In the 2011 published TASC Phase 3 study that evaluated cytisine versus placebo in 740 primarily moderate-to-heavy smokers treated for 25 days in Poland, the sustained 6-month abstinence rate was 10.0% in the cytisinicline arm compared to 3.5% in the placebo arm ($P<0.001$). In the 2014 published Phase 3 study that evaluated cytisinicline for 25 days versus nicotine replacement therapy (NRT) for 8 weeks in 1,310 adult daily smokers in New Zealand, the continuous six-month abstinence rate was 22% in the cytisinicline arm compared to 15% in the NRT arm ($P=0.002$).

Data from the international EAGLES trial (N=8120) were used to assess predictors for continuous smoking abstinence outcomes from Weeks 9-24. These analyses provided clear evidence that US origin was associated with lower success rates of stopping, regardless of treatment (varenicline, bupropion, or NRT). The continuous abstinence rates from 9-24 weeks in the US were 16.1%, 11.4% and 10.6% for varenicline, bupropion, or NRT, respectively, compared to 6.7% (95% CI: 5.3-8.4%) for placebo treatment. The odd ratios (OR) for these treatments in the US were 2.66, 1.78, and 1.64, respectively. The lower success rate in US smokers supports the view that smokers in the US may have particular characteristics that make it more difficult for them to stop smoking.

The trial size for this study is specified as 250 subjects per arm. The assumed control arm probability of success (continued abstinence to Week 24) is 0.07 (7%). The hypothesized experimental arm minus control arm probability difference is specified as 0.12 (12 points), corresponding to a hypothesized odds ratio of 3.116 (eg, 7% for placebo vs 19% for cytisinicline treatment). The significance level to be used is adjusted from the overall type I error probability of one-sided 0.025 to one-sided 0.0125 using the Bonferroni method to control for multiplicity. The statistical operating characteristics for each comparison are illustrated using simulation of Fisher's exact test with 10,000 replicates. These specifications are consistent with 95.7% power for each comparison with, conditional on 0.07 control arm probability outcome, an odds ratio critical region of ≥ 1.83 , corresponding to a critical difference of ≥ 0.051 (7% for placebo vs 12% for cytisinicline treatment).

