4.1.2. Secondary Efficacy Endpoints

There are 3 secondary efficacy objectives, 2 objectives for continuous abstinence through to Week 24 and 1 objective for assessing reduction in risk of relapse for Arm C compared to Arm B (eg, once achieving successful abstinence at Weeks 3-6, whether there is a greater chance of being relapse-free, if the subject continues on treatment for an additional 6 weeks compared to being switched to placebo).

The continuous abstinence through Week 24 success endpoint (secondary objectives 1 and 2) and the reduction in risk of relapse (relapse free) through Week 24 endpoint (secondary objective 3) must be defined separately for each of the three secondary efficacy comparisons because of differences in the primary evaluation timing, that is, Weeks 3-6 for the Arm A versus Arm B comparison and Weeks 9-12 for Arm A versus Arm C comparison, and a set evaluation time of abstinence at Weeks 3-6 for the Arm B versus Arm C followed by a comparison of reduction in risk of relapse (eg, relapse free after Weeks 3-6 successful abstinence). It is important to note that the data collected, and the schedules of collection, are identical for all arms.

The following operational details are applicable to these secondary efficacy comparisons:

- Being abstinent requires meeting both a self-reported criterion and a biochemical verification. The beginning of self-reported abstinence is Week 3 to Week 6 for comparisons of Arm A and Arm B and Week 9 to Week 12 for comparison of Arm A and Arm C. For comparison of Arm C to Arm B, the failure of self-reported abstinence starts at Weeks 3-6 for both Arms B and C.
- Self-reported abstinence over the Week 16 to Week 24 Follow-up period will be assessed using the Russell Standard¹ which allows up to a total of 5 cigarettes to be smoked in order to be regarded as abstinent or without relapse.
- Biochemical verification of non-smoking status is defined by a carbon monoxide concentration in exhaled breath of less than 10 ppm.

Subjects not observed to meet all success criteria will be regarded as non-success relative to the secondary efficacy outcome. Non-success will have two types: (1) subjects with adequate data

that fail to meet the above criteria, and (2) subjects having insufficient data to be assessed as a success.

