4.1.2.2. Reduction in Risk of Relapse (Relapse-Free)

For the comparison of Arm C to Arm B (secondary objective 3), relapse free (success of not having relapsed) from Weeks 3-6 through to Week 24 will be defined as having the following observed after initial abstinence (ie, primary success criteria) is determined from Weeks 3-6:

- At the Week 12 visit, subject self-report of abstinence (relapse-free) since the last clinic visit together with biochemical verification of abstinence, and
- Self-reported abstinence (relapse-free) during the Week 16 to Week 24 Follow-up period, defined as smoking up to a total of 5 cigarettes at the attended Week 16, Week 20, and Week 24 visits together with biochemical verification of abstinence at each attended visit. (Only one visit, either Week 16 or Week 20, is allowed to be missing.)

Subjects not observed to meet the above success criteria will be regarded as having relapsed to the secondary efficacy 3 outcome. Non-success or relapse will have two types: (1) subjects with adequate data that fail to meet the above criteria, and (2) subjects having insufficient data to be assessed as a success. Note: subjects not abstinent at Week 6 (eg, Weeks 3-6) will be regarded as having already relapsed.

Statistical methods for the reduction in risk of relapse (relapse free) endpoint are described in Section 10.1.3.

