10.1.3. Secondary Efficacy Analysis

The three secondary efficacy objectives are stated in Section 3.2. The secondary efficacy endpoints (continuous abstinence, risk of relapse [relapse free]) are described in Section 4.1.2.

The analysis for secondary objectives 1 and 2 will be done only if the corresponding primary comparison passes statistical criterion.

Two between-arm comparisons are planned for secondary objectives 1 and 2:

- Continuous abstinence from Week 6 to Week 24: Arm B (cytisinicline 6 weeks) vs Arm A (placebo)
- Continuous abstinence from Week 12 to Week 24: Arm C (cytisinicline 12 weeks) vs Arm A (placebo)

Each continuous abstinence endpoint is binary (success, failure). Note: For the secondary analyses, smoking abstinence during the follow up period only (Week 16 to Week 24) followed the Russell Standard of allowing up to 5 cigarettes and still be regarded as abstinent/success. Each analysis will then compare the treatment arms in terms of the proportion of subjects classified as a success using the same statistical methods as described above for the primary endpoint.

The analysis for secondary objective 3 will be conditional and performed only if both primary comparisons 1 and 2 pass statistical criterion. One between-arm comparison is planned for secondary objective 3.

- Reduction in Relapse from Week 6 to Week 24: Arm C (cytisinicline 12 weeks) vs Arm B (cytisinicline 6 weeks)

This endpoint is binary (relapsed, without relapse). The treatment arms will be compared in terms of the proportion of subjects without relapse (relapse-free) using the same statistical methods as described above for the primary endpoint.

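### Secondary objective 3 is framed as relapse among Weeks 3-6 abstainers but tested as a composite in all randomized Arm B and C subjects, which mislabels the result and costs power

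*Protocol*

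**What the plan says.** The documents describe objective 3 in two ways.

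- **Conditional.** The Rationale in the Protocol Synopsis says that relapse risk from Week 7 to Week 24 will be compared between C and B for subjects who achieved abstinence in Weeks 3-6. SAP 4.1.2 gives the same reading as an example: "once achieving successful abstinence at Weeks 3-6, whether there is a greater chance of being relapse-free" if treatment continues for six more weeks.
- **All randomized.** Protocol 16.4 states "Subjects not abstinent at Week 6 will be regarded as having relapsed" and adds "The analyses associated with these three objectives will be done as Intent-to-Treat (ITT) analyses". SAP 4.1.2.2 repeats the rule: "subjects not abstinent at Week 6 (eg, Weeks 3-6) will be regarded as having already relapsed". SAP 10.1.3 says "The treatment arms will be compared in terms of the proportion of subjects without relapse (relapse-free) using the same statistical methods" as for the primary endpoint, that is, the exact test stratified by site.

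The regimens are in Protocol 7.2: "Arm B subjects will take one cytisinicline tablet at each dosing per day for the first 6 weeks followed by one placebo tablet" and "Arm C subjects will take one cytisinicline tablet at each dosing per day for 12 weeks". They do not differ until Week 7.

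A comparison of C with B among Weeks 3-6 abstainers is also planned, as Other objective 7 (Protocol 6.3, SAP 3.3). It is exploratory and has no multiplicity protection (Protocol 16.6, SAP 10.2).

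**The concern.** Objective 3 is the only alpha-protected test of whether 12 weeks of drug holds abstinence better than 6 weeks. Under SAP 10.1.1 it is reached with protection only after both primary comparisons and both continuous-abstinence secondaries succeed.

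Subjects not abstinent at Weeks 3-6 cannot be successes in either arm, whatever they receive from Week 7. Counting them as relapsed has two effects. The reported relapse proportion would be made up largely of people who had not met the abstinence criterion in the first place. Chance differences between B and C in early quitting also enter the comparison as noise.

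The usual objection to conditioning on a post-randomization status is that treatment may have influenced it differently in the two arms. That objection has little force here, because both arms have the same blinded regimen until the end of Week 6.

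**Working it through.** **1. The plan's own figure.** Protocol 16.5: "The trial size for this study is specified as 250 subjects per arm"; 7% vs 19%; one-sided 0.0125; Fisher's exact test; stated power 95.7%. Full enumeration gives 95.75%, so the figure reproduces. It concerns cytisinicline vs placebo. No power is stated for C vs B.

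**2. Set-up for objective 3.** Let a be the proportion abstinent at Weeks 3-6 (the same in B and C, since the regimen is the same), and qB, qC the proportions of those who stay relapse-free to Week 24. Alpha is one-sided 0.025 (SAP 10.1.1).

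- Planned test: Fisher's exact test, 250 per arm, a×qB vs a×qC.
- Conditional test: Fisher's exact test, 250×a per arm, qB vs qC.

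**3. Assumed inputs.** None of a, qB or qC is in the documents. The nearest anchors for a are the ORCA-1 3 mg TID results (Protocol 4.3), 30% continuous abstinence at Weeks 5-8 and 50% point abstinence at Week 4, and the hypothesized 19% in Protocol 16.5. I take 30% as central and 19% to 50% as the range.

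**4. Example.** For a = 0.30, qB = 0.40, qC = 0.60: the planned test compares 0.30×0.40 = 12% with 0.30×0.60 = 18% at 250 per arm, power 42%. The conditional test compares 40% with 60% at 250×0.30 = 75 per arm, power 66%. Letting the number of abstainers vary at random lowers the latter to 63%. Relative loss is 1 − 42.4/66.3 = 36%, or 33% with random subset size.

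**5. Range, 20-point difference** (Fisher, fixed subset size, site strata ignored):

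| Abstinent at Weeks 3-6 | Relapse-free, B vs C | Planned | Conditional | Relative loss |
|---|---|---|---|---|
| 30% | 20% vs 40% | 60% | 71% | 15% |
| 30% | 30% vs 50% | 49% | 67% | 26% |
| 30% | 40% vs 60% | 42% | 66% | 36% |
| 30% | 50% vs 70% | 37% | 67% | 44% |
| 40% | 20% vs 40% | 75% | 84% | 11% |
| 40% | 40% vs 60% | 57% | 79% | 28% |
| 40% | 50% vs 70% | 51% | 79% | 35% |

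Over a = 19% to 50% and a wider set of relapse-free pairs, the relative loss runs from 2% (a = 50%, 30% vs 60%: 97.8% vs 99.7%) to 59% (a = 19%, 60% vs 80%: 20.3% vs 49.0%). The planned test had the lower power in every case.

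**6. Why.** For the same underlying effect, the efficiency of the planned test relative to the conditional one is approximately (1 − q)/(1 − a×q), with q the average relapse-free rate. At a = 0.30 and q = 0.50 this is 0.50/0.85 = 0.59. The loss grows as a falls and as q rises.

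**7. With site strata.** Simulating the exact test with 17 sites (the protocol expects 15-19) for the example in step 4 gives about 42-44% as planned, 58-61% with site-by-status strata, and 62-65% among abstainers without site strata. With no true difference, all three reject in about 1.4-2.1% of trials, below the nominal 2.5%.

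**8. No one is dropped by stratifying.** In a non-abstinent stratum the number of successes is zero in both arms by definition. Such a stratum contributes nothing to the exact conditional test or to the Mantel-Haenszel odds ratio. Stratifying by site and status therefore gives the same p-value as a site-stratified test among abstainers.

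**The case against.** The rule is deliberate and openly stated. It is part of the objective itself in both documents and is described as intent-to-treat. How many of all randomized smokers quit by Weeks 3-6 and stay quit is a legitimate question, in line with objectives 1 and 2. The SAP's conditional wording is only an example in parentheses. Chance differences in early quitting are random error that the test already allows for. The abstainer comparison is planned as Other objective 7, and SAP 10.2.8 summarizes time to failure by arm in the same subset.

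Most of this stands. A reader might infer that the planned test is biased or inflates type I error; the null results above do not support that. A reader might also infer that the relapsed group consists of people who never quit. SAP 4.1.1 shows otherwise: one reported cigarette or a CO reading of 10 ppm or more at a Weeks 3-6 visit, an unknown status at Week 3 or Week 6, or a later quit is enough to fail. In ORCA-1, 50% were abstinent at Week 4 and 30% over Weeks 5-8.

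One further limit is fair. The Week 6 visit is Day 42 ±1, so a Day 43 visit can follow the change of regimen by about a day. Weeks 3-6 status is essentially, not strictly, fixed before the arms diverge.

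What the objection does not remove is the mismatch between the Synopsis and Protocol 16.4, the label of relapse on a composite, and the fact that the more informative version of the comparison has no alpha.

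**Conclusion.** The point holds as a matter of labelling and efficiency. Objective 3 tests a composite, is called reduction in risk of relapse, and has less power than the comparison that its own framing describes.

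With 30-40% abstinent, a 20-point difference and relapse-free rates between 20% vs 40% and 50% vs 70%, the relative loss is roughly 10-45%. Across the wider assumptions it is about 2-59%. A reader might take a loss of about a third as a property of the plan. It is one scenario (30% abstinent, 40% vs 60%), and the documents contain no rates from which a single figure could be derived. The type I error of the planned test is controlled. This is a cheap improvement, not a defect that undermines the trial.

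**What to change.** Before unblinding, and for objective 3 only:

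- Add Weeks 3-6 abstinence status as a stratifier to the exact test of C vs B. This in effect moves the comparison in Other objective 7 to the alpha-protected position. Keep the relapse-free criteria of SAP 4.1.2.2.
- Report the relapse proportion by arm among subjects abstinent at Weeks 3-6.
- Keep the all-randomized comparison as supportive, named as abstinent at Weeks 3-6 and relapse-free to Week 24.
- State the power for objective 3 with its assumed rates.
- Amend Protocol 16.4 and SAP 4.1.2.2 and 10.1.3 together, and reconcile the Synopsis Rationale with Protocol 16.4. Protocol 16.3.1 and 16.4 carry the site stratifier and the common model over to the secondary objectives, so an SAP change alone is not enough.

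The cost is wording, one stratifier and a new pooling rule. SAP 10.1.2 pools only sites with fewer than 2 subjects in any treatment arm, which does not cover sparse site-by-status cells. With 17 sites and 30% abstinent there would be about 250×0.30/17 = 4.4 abstainers per arm per site. By a Poisson approximation, about 13% of sites would have fewer than 2 in B or in C. Either define pooling on abstainer counts or drop site stratification for this comparison. If the composite is preferred as the protected test, renaming it and reconciling the passages is the minimum.

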16.4.1. Analysis of Secondary Outcomes

There are 3 secondary efficacy objectives, 2 objectives for continuous abstinence and 1 objective for reduction in risk of relapse. The continuous abstinence through Week 24 success outcome (secondary objectives 1 and 2) and relapse-free through Week 24 (secondary objective 3) must be defined separately for each of the three associated comparisons because of differences in the primary evaluation timing, that is, Weeks 3-6 for the Arm A versus Arm B comparison and Weeks 9-12 for Arm A versus Arm C comparison, and a mixed primary evaluation time for the Arm B versus Arm C comparison. It is important to note that the data collected and the schedule of collection are identical for all arms.

The following operational details are applicable to these secondary comparisons:

- Being abstinent requires meeting both a self-reported criterion and a biochemical verification. The beginning of self-reported abstinence is Week 3 to Week 6 for comparisons of Arm A and Arm B and Week 9 to Week 12 for comparison of Arm A and Arm C. For comparison of Arm B to Arm C, the failure of self-reported abstinence starts at Week 6 for both Arms B and C.
- Self-reported abstinence over the Follow-up Weeks 16-24 period will be assessed using the Russell Standard¹⁷ to be regarded as abstinent or without relapse.
- Biochemical verification of non-smoking status is defined by a carbon monoxide concentration in exhaled breath of less than 10 ppm.

Subjects not observed to meet all success criteria will be regarded as non-success relative to the secondary efficacy outcome. Non-success will have two types: (1) subjects with adequate data that fail to meet the above criteria, and (2) subjects having insufficient data to be assessed as a success.

16.5. Study Size

In the 2011 published TASC Phase 3 study that evaluated cytisine versus placebo in 740 primarily moderate-to-heavy smokers treated for 25 days in Poland, the sustained 6-month abstinence rate was 10.0% in the cytisinicline arm compared to 3.5% in the placebo arm ($P<0.001$). In the 2014 published Phase 3 study that evaluated cytisinicline for 25 days versus nicotine replacement therapy (NRT) for 8 weeks in 1,310 adult daily smokers in New Zealand, the continuous six-month abstinence rate was 22% in the cytisinicline arm compared to 15% in the NRT arm ($P=0.002$).

Data from the international EAGLES trial (N=8120) were used to assess predictors for continuous smoking abstinence outcomes from Weeks 9-24. These analyses provided clear evidence that US origin was associated with lower success rates of stopping, regardless of treatment (varenicline, bupropion, or NRT). The continuous abstinence rates from 9-24 weeks in the US were 16.1%, 11.4% and 10.6% for varenicline, bupropion, or NRT, respectively, compared to 6.7% (95% CI: 5.3-8.4%) for placebo treatment. The odd ratios (OR) for these treatments in the US were 2.66, 1.78, and 1.64, respectively. The lower success rate in US smokers supports the view that smokers in the US may have particular characteristics that make it more difficult for them to stop smoking.

The trial size for this study is specified as 250 subjects per arm. The assumed control arm probability of success (continued abstinence to Week 24) is 0.07 (7%). The hypothesized experimental arm minus control arm probability difference is specified as 0.12 (12 points), corresponding to a hypothesized odds ratio of 3.116 (eg, 7% for placebo vs 19% for cytisinicline treatment). The significance level to be used is adjusted from the overall type I error probability of one-sided 0.025 to one-sided 0.0125 using the Bonferroni method to control for multiplicity. The statistical operating characteristics for each comparison are illustrated using simulation of Fisher's exact test with 10,000 replicates. These specifications are consistent with 95.7% power for each comparison with, conditional on 0.07 control arm probability outcome, an odds ratio critical region of ≥ 1.83 , corresponding to a critical difference of ≥ 0.051 (7% for placebo vs 12% for cytisinicline treatment).

The study size is designated for approximately 750 subjects (250 subjects per arm). However, if higher than expected early treatment discontinuations ($>5\%$) occur before completion of 6 weeks study treatment due to reasons other than adverse events, additional enrollment may be allowed up to 10% or 75 subjects.

